Aim 3. Pilot test measures to assess treatment outcomes within patients who self-identify as Hispanic/Latino at a health care clinic in New York and estimate measurement parameters for future efficacy testing (means and standard deviations).

Aim 4. Measure level of acculturation and rates of bi-directional travel in this study population.

Aim 5. Generate an explanatory model of HIV infection among patients in this clinical context and explore how it may be used to guide HIV-related communication using infographics.

Study Design

To complete the study aims, a mixed methods study will be conducted. The components of this study include:

- 1) One design session with health care providers at CHP-NYP
- 2) A single group pretest/posttest study design will be used to pilot test the infographic intervention
- 3) In-depth interviews with two stakeholders
 - a. Patient participants who receive the intervention
 - c. Members of the clinical team at CHP-NYP

An initial design session will be conducted to learn how to adapt infographics that were designed in the DR to be useful and relevant in a clinical setting in New York City. Changes will be incorporated into the designs and then the intervention will take place over the subsequent 8 months. During the intervention, patient participants will receive information using the infographics during study visits, which will take place after their normal visits to CHP-NYP. Baseline data will be collected from patient participants at enrollment and at 3- and 6-month follow up visits. In-depth interviews will be completed with a selection of patient participants to develop an explanatory model of HIV infection and HIV-related communication using infographics. Individual interviews will also be conducted with additional members of the CHP-NYP clinical team to explore factors related to intervention implementation.

Statistical Procedures

1) Design session with health care providers (N ≤ 10)

The audio recording of the design session with health care providers will be transcribed and analyzed with conventional content analysis to extract key points and recommended changes to infographic designs (Aim 1).

2) Single group pretest-posttest study design (N = 30)

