Descriptive statistics (means, standard deviations) will be calculated for all participant demographics. Responses to open-ended questions in baseline and follow up questionnaires will be grouped according to meaning and then, needed changes in infographic design or clinical processes will be determined (Aim 2). Scores on the acculturation scale will be calculated according to published recommendations (Aim 4).^{36,37} Mean scores and standard deviations will be calculated for each additional scale included in the follow up assessments and the change in mean scores between baseline and follow-up assessments determined (Aim 3). To take into account sex as a biological variable (NOT-OD-15-102), mean scores between male and female participants will be compared. Cronbach's alpha will be used to compare the reliability of measures with reported values and to support the assertion that these tools can be used within this population. Data collected will also be used to estimate parameters for use in determining effect sizes, which will be corrected for the bias inherent in small samples,³⁸ and reported as relative risks for categorical outcomes and as Cohen's D for continuous outcomes which will enable a more precise power calculation for subsequent study phases (Aim 3).

3.a.) Individual interviews with patient study participants (N ≤ 25)

We will conduct semi-structured individual interviews using an iterative interview guide (see attached interview guide) developed following the recommendations of Kallio 2016 which includes 1) internal testing by the research team; 2) expert assessment by specialists outside the research team; and 3) field-testing with the potential study participants.³⁹ Depending on when saturation is reached, up to 30 in-depth interviews will be conducted with participants who are enrolled in the study.

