Study team members who will administer the intervention will have a training regarding how guide patient education with infographics using the adherence counseling format that is used at CHP-NYP and will review principal components of intervention fidelity, including how to maintain it.^{47,48} During the intervention period, after normal clinic visits, study team members will guide education using the laminated, paper-based set of infographics developed in preliminary studies. Infographics will be available in both English and in Spanish and will provide a visual representation of the pertinent information to be included in clinical conversations. Intervention fidelity will be verified by audio recording up to one-half of total intervention visits with patient permission as is detailed in the informed consent document. Members of the study team will listen to audio recordings to confirm the other team member is using infographics during visits as specified in the intervention training, that both study team members are using them in the same way, and that they are delivering the intervention consistently across visits. Study team members will complete a second training session after the baseline visits to revisit main points that need to be addressed while administering the intervention and address any concerns that arise during the initial intervention visits. Patient participants will be asked about study team members use of infographics during follow up assessments.

Participant eligibility will be verified by clinic staff through electronic health records during team huddles that take place in the mornings on study days. A list of eligible participants will be provided to the health care providers who are seeing patients that day. The provider will then assess potential participant interest using the attached recruitment script and refer those who are interested in participating to an on-site study team member. That team member will then further introduce the study and then if a participant is interested, complete the informed consent process.

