After completing informed consent, patient participants will complete a baseline assessment using REDcap on an encrypted tablet with the help of a study team member prior to intervention administration (Table 1). Patient participants will then receive the intervention during study visits, which will take place after participants' normally scheduled appointments at baseline, 3- and 6-month visits. They will complete a follow up assessment at their visits closest to 3- and 6-months following their baseline visit. Study team members will extract information from patient medical records (CD4 count, viral load, current ART etc.) at each data collection time point. Patient participants will receive reminder phone calls prior to each of their study visits using the attached reminder phone call script. Time intervals were selected as CD4 count and viral load may change as early as three months after ART initiation.⁴⁹⁻⁵¹ Study team members will time how long it takes to administer the intervention.

Following their six-month study visit, participants will be asked to participate in an in-depth interview. At the end of the study, additional members of the clinical team will be interviewed to assess feasibility of infographic use in this clinical setting.

Table 1. Summary of research activities

Date(s)	Study point	Participants	Activities
July 2019	Design Session	• Members of clinical team	• Two hour design session
September 2019	Study team member training	• Study team members	• Two-hour training on how to use infographics
September/October 2019	Enrollment	• Patients • Study team	• Health literacy assessment • Baseline assessment • Exposure to intervention • CD4 & viral load extracted
December 2019/January 2020	3-month visits	• Patients • Study team	• Exposure to intervention • Follow up assessment • CD4 & viral load extracted
March/April 2020	6-month visits	• Patients • Study team	• Exposure to intervention • Follow up assessment • CD4 & viral load extracted
March – May	In-depth interviews	• Patients	• Follow up assessment • CD4 & viral load extracted
April/May	In-depth interviews	• Members of the clinical team	• Individual interviews with team members

Measures

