Outcome selection was guided by a conceptual model to theoretically guide communication studies.^{52,53} This model illustrates pathways through which clinician-patient communication may influence health outcomes in the short (proximal), medium (intermediate), and long-term. Primary outcomes of CD4 count and viral load will be collected from patient medical records at each study visit. Measures of information recall/comprehension, satisfaction with care,⁵⁴ self-efficacy to manage HIV,⁵⁵ adherence,⁵⁶ health related quality of life,⁵⁷ and health status (self-reported status and CD4 count and viral load) will all be included in the baseline and follow up assessments.

Baseline assessments will collect demographic information, assess level of acculturation,³⁷ evaluate health literacy level,⁵⁸ and contain a measure for each outcome.

Follow up assessments for PLWH will include the outcome measures as well as open-ended questions exploring the usability of infographics, satisfaction with designs and recommendations for improvement. Open-ended questions regarding interventionists' communication strategies and intervention delivery will be included to assess providers' communication variability.

In-depth interviews with PLWH. To describe PLWH's perceptions of HIV-related communication in a clinical setting and how it may be influenced by infographic use, directed content analysis guided by

McGuire's Classic Input-Output Framework for Constructing Persuasive Messages will be used.⁵⁹ In-depth interviews will be conducted using a semi-structured interview guide in a private setting by a study team member and will be audio-recorded and transcribed.

In-depth interviews with clinical care team. To learn more about how this intervention was accepted and feasible at the clinic as a whole, interviews will be conducted with additional members of the clinical care team. Participants will complete a semi-structured interview containing questions on the following aspects of feasibility: acceptability, demand, implementation, practicality, adaptation, integration, expansion, and limited-efficacy testing⁶⁰ and questions elucidating feedback on infographic design and suggestions regarding their effective incorporation into clinical visits.

Each session will be audio recorded, later transcribed, and then analyzed to identify key features of the study that worked and what didn't work in order to better inform future efforts.

Recruitment and Consent

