adhered to in order to avoid any loss of confidentiality. An additional risk is that participants might feel uncomfortable if they are unable to answer some of the questions in the surveys. Prior to beginning data collection, all participants will be reminded they do not have to answer any question that makes them feel uncomfortable and that they may withdraw from the study at any point without any consequences whatsoever. During the study visits, a study team member will also be available in order to provide any help that does not lead participants to the correct answer. During in-depth interviews participants may feel discomfort discussing their HIV status. Prior to interviews, participants will be reminded that they do not have to answer any question that makes them feel uncomfortable and that they are free to leave the interview at any time without any consequences whatsoever.

Additionally, all study team members will be trained to identify signs of suicidal ideation and depression. Should they notice any of these signs while they are completing a study visit, or if participants are showing signs of discomfort, the study visit will be stopped immediately, and the participant will be referred to an appropriate mental health professional.

Potential Benefits

This study does not have any direct benefit to participants. However, participants are more likely to benefit from the health education provided because of the intervention. Additionally, by participating in this research, they will be able to actively contribute to improving the health care services that they and their peers receive.

Alternatives

This study does not present greater than minimal risks to participants. An alternative is to not participate in this research.

Data and Safety Monitoring

The safety of this study's data will be regularly monitored by the study team. Any breaches of the study protocol will be submitted to the IRB immediately.

Subjects

Inclusion Criteria

Adults (≥ 18 years of age) living with HIV, who self-identify as Hispanic/Latino, are English or Spanish Speaking, a new patient or a patient with a detectable viral load and plan to receive care at the NYP-CHP during the study period will be eligible for inclusion.

Exclusion are current pregnancy or inability to provide informed consent.

Study population characteristics

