Study participants will be adults (≥ 18 years of age) living with HIV, who self-identify as Hispanic/Latino, are English or Spanish Speaking, with a detectable viral load and plan to receive care at

the NYP-CHP during the study period. Participants are likely to be economically and educationally disadvantaged and non-English speaking.

Subject population justification

PLWH at NYP-CHP are likely to have lower levels of education and low health literacy and adherence to antiretroviral medications is a perpetual concern. Although a vulnerable population because they are living with a stigmatized health condition and are economically and educationally disadvantaged, their participation in this research is justified because it enables them to help design a tool and intervention that may help them to better manage their condition and improve the clinic services that they and their peers receive. Furthermore, if the target population of interventions is not included in the research design and evaluation phases, interventions may be ineffective and misguided.

Describe and justify reimbursement/compensation

Participants will receive \$25 in the form of a paycard for each of their study visits (three visits total). Participants who participate in the in-depth interviews will also receive a \$25 pay card for that visit. Providers involved in the intervention will be provided refreshments the two trainings on how to administer the intervention as well as during the semi-structured interview that they will complete at the end of the study.

References

2. Brown A, Hugo Lopez M. *Mapping the Latino Population, By State, County and City*. Washington DC2013.

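### For patients who enter on a detectable viral load, the qualifying chart value can also be the baseline of that primary outcome, so part of any fall among them can be regression to the mean

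*Combined protocol and SAP*

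**What the plan says.** - **Entry.** Subjects, Inclusion Criteria, admits "a new patient or a patient with a detectable viral load". The next subsection, Study population characteristics, describes participants as adults "with a detectable viral load and plan to receive care at" the clinic and does not mention the new-patient route. Neither gives a copies/mL limit or a maximum age for the qualifying result.
- **When entry is checked.** Procedures, Infographic intervention: "Participant eligibility will be verified by clinic staff through electronic health records during team huddles that take place in the mornings on study days". Consent, the baseline assessment and the first infographic session follow that day's appointment.
- **Where baseline comes from.** Same section: "Study team members will extract information from patient medical records (CD4 count, viral load, current ART etc.) at each data collection time point". The enrolment row of Table 1 lists this extraction. Measures adds: "Primary outcomes of CD4 count and viral load will be collected from patient medical records at each study visit".
- **Design and use.** Study Design: "A single group pretest/posttest study design will be used to pilot test the infographic intervention". Statistical Procedures, item 2, plans effect sizes, "reported as relative risks for categorical outcomes" and as Cohen's D for continuous ones, to inform the power of later phases. The only correction named is for small-sample bias.

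The documents do not ask for a new specimen at baseline, set a date window for the result, or separate the qualifying result from the baseline result.

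**The concern.** A viral load reading is the person's underlying level plus short-term and assay variation. Admitting people because a reading was above a limit over-represents readings that were high by chance on that occasion. If the same reading then starts the change, the next one is lower on average even when nobody has changed. A transient detectable value, or one already resolved by enrolment, would count as improvement.

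A randomised comparator would show the same drift and cancel it. This design has none, and a small-sample correction does not address selection. What is at stake is Aim 3: an effect size that includes this drift would make the next study too small. CD4 count is not an entry criterion, so the point concerns viral load.

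**Working it through.** **Can the two values coincide?** Eligibility is read from the electronic record in the morning of the study day. Baseline is extracted from the patient's medical record at the enrolment time point. If no newer result posts in between, both readings return the same number. The text permits this and does not require it.

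**Inputs.** From the documents: one group, N = 30, follow-up at 3 and 6 months. They give no SD, detection limit, test-retest correlation or share of new patients, so there is no stated figure to reproduce and the inputs below are assumptions.

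**Check 1, simulation with no true change.** True log10 viral load is normal with mean 1.5, 2.0 or 2.5 and SD 1.0. Within-person SD is 0.2, 0.3 or 0.5. Readings are floored at 20 copies, and a patient is selected if the first reading exceeds 50 copies. There are 2 million patients per scenario. The extremes of the nine scenarios are:

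| Scenario | Mean change, qualifying value to repeat | Undetectable on repeat |
|---|---|---|
| Mean 2.5, within-person SD 0.2 | -0.014 log10 | 4.1% |
| Mean 1.5, within-person SD 0.5 | -0.165 log10 | about 23.4% |

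If the change instead starts from a second reading, separate from the qualifying one, its mean is about 0.000 in all nine scenarios.

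**Check 2, less stable readings.** The test-retest correlation in check 1 is 1/(1 + w²), where w is the within-person SD: 1/1.04 = 0.96 for 0.2 and 1/1.25 = 0.80 for 0.5. A second set used total SD 1.0, correlation rho from 0.5 to 0.9, and 20% to 70% of the source population detectable at 50 copies. Without censoring,

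expected fall = (1 - rho) × SD × φ(a) / (1 - Φ(a)),

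where a is the standardised limit. Example: 20% detectable gives a = 0.842 and φ(a)/(1 - Φ(a)) = 0.280/0.20 = 1.40, so with rho = 0.7 the fall is 0.3 × 1.0 × 1.40 = 0.42 log10. With values below 50 copies set to the limit, the simulated fall is 0.17. Over the whole set the censored fall is 0.03 to 0.27 log10, a standardised paired change of about 0.06 to 0.46. With a separate baseline it is 0.00.

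**Dilution.** If one third of participants (assumed) entered as new patients unselected on viral load and did not change on average, the overall fall is two thirds of these values: 2/3 × 0.165 = 0.11 at the top of check 1, and 2/3 × 0.27 = 0.18 at the top of check 2.

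**Against sampling error.** With 30 patients, all in the detectable group, the standard error of the mean change under check 1 is 0.05 to 0.12 log10. The artefact is about 0.3 to 1.4 standard errors.

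**If detectability were analysed as a binary outcome.** With the qualifying value as baseline, 100% of this group is detectable at baseline by construction. A follow-up versus baseline relative risk of being undetectable would have a zero denominator. A relative risk of being detectable could not exceed 1, and with no true change it would be 1 - 0.041 = 0.96 to 1 - 0.234 = 0.77 under check 1.

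**The case against.** The strongest reply is that the coincidence is not established. Extraction takes place at the enrolment time point, after the clinic appointment. If blood is drawn at that appointment and its result is the one recorded, the artefact largely disappears. That stands, which is why the point is conditional. It does not dispose of the point, because the documents do not say that a specimen is taken then or which result counts.

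A reader might infer that the plan specifies a relative risk for viral suppression that cannot be computed. It does not: Statistical Procedures names no categorical outcome and no contrast, and viral load is not dichotomised for analysis anywhere. The zero denominator arises only if that analysis is chosen and the qualifying value is the baseline.

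A reader might also apply the 4% to 23% to all 30 participants. The documents give no split between new and detectable patients, so no head count follows. Under Inclusion Criteria the problem reaches only those who enter by detectability; under Study population characteristics it reaches everyone.

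Two further replies carry weight. This is an uncontrolled feasibility pilot, and the artefact is within about one standard error in most scenarios of check 1. And if a later study kept the same entry rule and chart-based baseline, the selected baseline mean and SD would be the values it needs. Both narrow the point to the change and its effect size. Since those are meant to feed a power calculation, a bias in a known direction is still worth removing.

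**Conclusion.** The point holds in conditional form. The plan lets a value selected for being detectable start the change in a primary outcome, with no comparator and no correction for selection. When that happens and nothing truly changes, the expected fall among patients who entered by detectability is about 0.01 to 0.17 log10, with 4% to 23% reading undetectable on repeat. Less stable readings raise the fall to as much as 0.27 log10. All these figures rest on assumed limits, means and variances; the artefact is small if viral load is very stable and is diluted by any new patients unselected on viral load. The documents do not show that the artefact will occur, and they do not support a claim about any particular number of patients. The change is worth making because the correction is cheap and the estimate is intended for reuse.

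**What to change.** 1. Use the qualifying result for eligibility only.
2. Define baseline viral load as the result of a routine specimen taken after the qualifying one and no later than the enrolment-day appointment, before the first infographic exposure. Extract it when it posts, for example at the 3-month chart review. A specimen from a later day would follow exposure and should not count as baseline.
3. Flag patients who have only the qualifying value. Report change with and without them, and note possible regression to the mean.
4. If suppression is reported, give the proportion undetectable at the new baseline and at each follow-up, with confidence intervals, among all participants with a separate baseline. Do not restrict to those detectable at the new baseline. That selects on a high reading again: under check 1, 2.3% to 14.7% would still read undetectable with no true change, more than half of the artefact (2.3/4.1 = 56%; 14.7/23.4 = 63%).
5. Reconcile Inclusion Criteria with Study population characteristics on the new-patient route, since this decides how many participants are affected.

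The cost is wording plus one later look at a chart that is opened anyway. No study blood draw is added, but the fix depends on a routine specimen being available, which the documents do not promise. Some patients may have none before exposure, which leaves fewer in the unflagged analysis. Improvement from starting ART or from usual care stays confounded with the intervention, because a separate baseline removes only the selection artefact.

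### The primary CD4 and viral load values are tied to the date of chart extraction and not to the date of blood draw, so a 3-month value may come from a specimen taken before any exposure

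*Combined protocol and SAP*

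**What the plan says.** The Measures section names the primary outcomes and their source: "Primary outcomes of CD4 count and viral load will be collected from patient medical records at each study visit". The Infographic intervention section (under Procedures) repeats the rule: "Study team members will extract information from patient medical records (CD4 count, viral load, current ART etc.) at each data collection time point". Table 1 says only that both values are extracted, at enrollment, at the 3- and 6-month visits, and again in the row for the March to May patient interviews.

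The study sessions are described as visits "which will take place after participants' normally scheduled appointments at baseline, 3- and 6-month visits". On follow-up timing: "They will complete a follow up assessment at their visits closest to 3- and 6-months following their baseline visit". No limits in days are given. The spacing is justified on laboratory grounds: "Time intervals were selected as CD4 count and viral load may change as early as three months after ART initiation". Table 1 puts enrollment in "September/October 2019", 3-month visits in "December 2019/January 2020" and 6-month visits in "March/April 2020".

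The combined protocol and SAP contains none of the following: a study-ordered draw, a window for the specimen date, an instruction to record that date, a rule for several results or no new result, or a requirement that a follow-up specimen postdate the baseline session.

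Under Statistical Procedures, the data are to yield relative risks and Cohen's D, corrected for small samples, for the power calculation of later study phases (Aim 3).

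**The concern.** The plan chose 3-month spacing because of how soon CD4 count and viral load can move. That argument needs specimens, not chart reviews, to be about three months apart. As written, a value is labelled 3-month because it was extracted at the 3-month visit, whatever the age of the blood behind it.

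Two distortions follow.

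- **Repeated specimen.** If no new result has been posted since baseline, the same specimen can serve as both the baseline and the 3-month value, and the change is exactly zero.
- **Old baseline.** If the baseline value is itself old, the change score includes whatever happened before the first session.

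Both enter the mean changes and effect sizes that Aim 3 hands to the next study.

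**Working it through.** The plan has no figure to reproduce: N = 30 is stated without alpha, power, effect size or SD. The inputs from the documents are the extraction rule, the visit rule and the Table 1 months. All other inputs below are assumptions.

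**1. What the calendar allows.** Taking the first and last days of the Table 1 months:
- Baseline to 3-month visit: 31 October to 1 December = 31 days; 1 September to 31 January = 152 days.
- Baseline to 6-month visit: 31 October to 1 March = 122 days; 1 September to 30 April = 242 days.
- 3-month to 6-month visit: 31 January to 1 March = 30 days; 1 December to 30 April = 151 days.

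These are outer limits, and choosing the closest visit should narrow them. The 3- and 6-month ranges still overlap from day 122 to day 152, before any lag between draw and visit.

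**2. How often the latest result could be too early.** Assume routine draws every L days at a random phase, immediate posting, and use of the latest result. The share of latest results older than a session held t days earlier is max(0, 1 − t/L).

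| Assumed L (days) | 3-month value predates baseline session (t = 91) | 6-month value predates baseline session (t = 182) | 6-month value predates 3-month session (t = 91) |
|---|---|---|---|
| 90 | 0% | 0% | 0% |
| 120 | 24% | 0% | 24% |
| 182 | 50% | 0% | 50% |
| 270 | 66% | 33% | 66% |
| 365 | 75% | 50% | 75% |

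A value older than all exposure is mainly a 3-month risk. At 6 months it needs draws more than 182 days apart. In this model, a 3-month value that predates baseline is the same specimen as the baseline value. If posting is delayed, a baseline-day draw could instead surface as the 3-month value: still before exposure, but not a repeat.

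A draw taken at the 3- or 6-month appointment precedes that day's session by design. That is not an error, since the value is meant to follow the earlier sessions.

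**3. Effect of repeats.** Assume a true mean fall of 1.0 log10 and SD of change 1.0, and let a share f have zero change. Then mean fall = 1 − f, and variance = (1 − f)(1² + 1²) − (1 − f)².

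| f | Patients of 30 | Mean fall | Variance | SD | Mean/SD |
|---|---|---|---|---|---|
| 10% | 3 | 0.9 | 1.80 − 0.81 = 0.99 | 0.995 | 0.90 |
| 30% | 9 | 0.7 | 1.40 − 0.49 = 0.91 | 0.954 | 0.73 |
| 50% | 15 | 0.5 | 1.00 − 0.25 = 0.75 | 0.866 | 0.58 |

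Without repeats the ratio is 1.00. It falls less than the mean because repeats also shrink the SD of change. The plan does not say which SD Cohen's D uses. With an unaffected raw SD, an assumed d of 1.0 would become 0.9, 0.7 and 0.5. A next-study sample size based on that d would grow by 1/(1 − f)², that is 1.23, 2.04 and 4.00 times.

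**4. Effect of an old baseline.** Observed change = (follow-up − value at first session) + (value at first session − old value). The second term is drift before exposure. If viral load was already falling, it exaggerates the fall; if rising, it hides some of it. The sign cannot be known from the documents, and the eligibility criteria admit both new patients and patients with a detectable viral load.

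**The case against.** A reader might infer that the plan orders staff to use whatever result is in the chart on the visit day. It does not. It never says that the latest result is used, or that a pending result may not be added later. The data-collection form is not among the documents, so a specimen-date field may exist. The clinic may also draw blood at or near most appointments, which would make stale values rare. These points stand: the mechanism is a permitted reading, not a stated rule, and its frequency is unknown.

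Table 1's further extraction at the patient interviews could pick up 6-month results that were pending on the visit day. This also stands, but it covers only those interviewed (at most 25 by that section's heading, up to 30 by its text). It does nothing explicit for month 3, and the plan does not say which extraction supplies the 6-month value.

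A reader might also infer that 3- and 6-month values are equally exposed, or that the bias always shrinks the effect. Neither holds. A 6-month value older than all exposure needs about six months without a new posted result, and an old baseline can inflate the change.

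Finally, this is a single-group pilot with no hypothesis test specified for these outcomes. That limits the harm without removing it, because estimating parameters for later testing is a stated aim.

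**Conclusion.** The point holds as a missing specimen-date rule for the primary outcomes. Followed as written, the plan allows a pre-exposure or repeated specimen to be labelled a 3-month value, and a specimen older than the 3-month session to be labelled a 6-month value. Repeats pull the mean change toward zero; an old baseline can push it either way, so the net direction is unknown.

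The documents do not support any estimate of how often this would happen. The fall from 1.00 to 0.90, 0.73 or 0.58 rests on an assumed 1.0 log10 fall, an assumed SD of change of 1.0 and assumed repeat shares of 10%, 30% and 50%. The table of draw intervals rests on assumed regular draws at a random phase. CD4 count is not quantified. What is at stake is the pilot's change scores and the planning parameters derived from them.

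**What to change.** Replace visit-by-visit extraction of the two primary values with one dated extraction after the last visit. Table 1 already lists a further extraction at the March to May interviews; extend it to all patients and take every CD4 and viral load result with its specimen date. Then assign values as follows:

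- **Baseline:** last specimen on or before the first session, within a pre-stated look-back.
- **3 and 6 months:** specimen nearest day 90 and day 180, drawn after the previous session, in non-overlapping windows. One option is to split at day 135, the midpoint of 90 and 180.
- **Reuse and gaps:** no specimen is used twice, and the value is missing if none qualifies.
- **Reporting:** give the draw-to-visit interval and the number missing at each time point.

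The look-back and the outer window limits should be stated before the data are examined. A rule is also needed for a 3-month visit held after day 135, which Table 1 permits: a draw at that appointment would fall in the 6-month window yet precede the 3-month session.

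The cost is a few more data fields, a written assignment rule, and some missing time points, which will be felt at N = 30. Those gaps would be visible, whereas a stale value is not. Nothing changes in care or in when blood is drawn.
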